**The Effects of Two Different Electrical Stimulation Methods on the Pain Intensity of
the Patients Who Had Undergone Abdominal Surgery With a Midline Incision:
Randomized Controlled Clinical Trial**

[name]

[name], Professor

Document Date: May 1, 2015

The effects of two different electrical stimulation methods on the pain intensity of the patients who had undergone abdominal surgery with a midline incision: Randomized Controlled Clinical Trial

**[name]
[name]**

This study was conducted as a randomized controlled trial. The primary outcome measures were the effects of TENS and TAES on pain and analgesic drug consumption in patients who had undergone abdominal surgery with a midline incision. Secondary outcome measures were the effects of TENS and TAES use on respiratory functions, vital signs, nausea and vomiting status, dizziness, antiemetic drug consumption, and saturation

Study setting

This study was conducted at the Department of General Surgery of the Gülhane Training and Research Hospital in Ankara, Turkey between May 2015 and November 2016.

Participants

The population consisted of General Surgery patients who underwent planned abdominal surgery with a midline incision between May 2015 and November 2016. The study sample comprised patients who underwent abdominal surgery with a midline incision due to problems related to colorectal cancer and stomach cancer. The principal investigator evaluated patients awaiting abdominal surgery with a midline incision in the hospital room the day before the surgery to ensure that the patients qualified for the study in accordance with the eligibility criteria.

Inclusion criteria

Patients who had an American Society of Anesthesiologists (ASA) score of I-II, were aged over 18 years, who could read and write Turkish, who were scheduled to undergo elective abdominal surgery with a midline incision for a diagnosis of stomach or colorectal cancer, and without any impairment of vision, hearing or speech were included in the study.

Exclusion criteria

Patients who had a pacemaker, whose skin integrity around the incision was degraded, had a cognitive disorder, had a history of chronic pain, or were suffering from neurological, renal, cardiac or pulmonary disorders that could affect the test results, and patients with an opioid addiction, those who had previously undergone electrical stimulation treatment, morbidly obese subjects and patients using

psychoactive drugs were excluded.

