Randomization

To determine the groups, randomization was performed with a web-based randomization system with the help of a computer by researchers. A block randomization list was obtained for 3 groups. TENS was implemented to the incision circumference of the patients in the first group and to the acupuncture points of the patients in the second group with no treatment being implemented to the control group.

The interventions

The standard anesthesia protocol was implemented to all patients suitable for the study. All of the patients included in the study were administered 2 mg midazolam IV 5 minutes before the operation as premedication, after the peripheral vein was accessed. Once the ECG, noninvasive blood pressure, and pulse oximeter monitorization was started, preoxygenization was provided and anesthesia induction conducted intravenously with propofol 2-2.5 mg /kg, rocuronium bromide 0.6 mg /kg, and fentanyl 2 mcg /kg. This was followed by oral tracheal intubation 90 seconds after 100% O₂ at 4 l/min was started. After endotracheal intubation, the inhalation agent desflurane was set at 6% concentration. All patients were administered 0.2 mg/kg rocuronium bromide IV at 30-minute intervals and IV remifentanil was adjusted to 0.25 mcg/kg/min. All patients were administered intraoperative ranitidine HCl 20 mg and metoclopramide 10 mg. After the last skin suture was placed, the inhalation agent and remifentanil infusion were terminated. Once spontaneous breathing started, the muscle relaxant agent was antagonized (neostigmin 0.05 mg/kg, atropine 0.015 mg/kg) and the patient was extubated when spontaneous breathing and adequate muscle strength were present.

A standard analgesia protocol for post-operative pain control was used in all patients included in the study. The Patient Controlled Analgesia infusion was administered to the patients for 48 hours. The patients were provided a total of 500 mg Tramadol HCl Patient Controlled Analgesia infusion intravenously (IV) at a concentration of 5 mg/ml, an infusion dose of 5 mg/hr, a bolus dose of 20 mg, and a 150 mg per 4 hour limit with a 30 minute lock-in time. Dexketoprofen Trometamol vial IV and/or 50 mg Pethidine HCl IM were used as rescue analgesic drugs.

A standard antiemetic protocol was used for all patients after surgery. If they had nausea, 4 mg/2 ml ondansetron was administered intravenously.

First Intervention Group: The Patient Controlled Analgesia infusion was started right after the

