Pain: VAS with a range of 1-10 points was used while the pain levels of all patients were evaluated. Pain levels of all patients were evaluated at rest.

Analgesic drug consumption: All patients were administered IV Contramal infusion with PCA for the first 48 hours. Dexketoprofen Trametamol vial IV and/or 50 mg. Pethidine HCl IM was used as the rescue analgesic.

Nausea severity: VAS with a range of 1-10 points was used while evaluating the nausea severity of all patients .

Vomiting: The number of times the patients vomited was recorded.

Antiemetic drug consumption: The antiemetic drug amount administered to the patients was recorded in mg.

Pulmonary function tests: The pulmonary functions of the patients were evaluated with a portable spirometer. PEF and FVC values were recorded. The measurement of respiratory functions was performed with the patient wrapping the disposable mouthpiece well with the lips during the measurement. The patient was asked to breathe deeply and exhale suddenly and quickly. This process was repeated three times and the best performance was taken as the base value.

Sample size: The software package G-power 3.1.3. was used to conduct a prior power analysis to calculate the number of participants required. Sixteen participants were required to detect an effect size of 1.4 at 80% power. The alpha level used to define significance was 0.05.

Blinding: Because the patients and data collector were aware they were implementation electrical stimulation or not, there was no blinding to the study.

Data collection: Data collection was started on the day before the patients underwent surgery and finished on the 2nd day after surgery.

Preoperative data collection: The characteristics of the patients and ASA classifications, vital signs and respiratory functions were evaluated one day prior to the surgery.

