Postoperative data collection: The medical information of the patients was recorded within the initial 48 hours after the surgery. Vital signs, respiratory functions, pain levels, nausea severity, vomiting status, dizziness status, analgesic and antiemetic drug consumption of all patients included in the study were recorded. Vital signs and pain levels of the patients in the control group were evaluated at the post-operative 30th min. and 2,18,22,42, and 46th hours. Vital findings and pain levels of the patients who were included in the intervention groups before and 30 minutes after the implementation were evaluated. All evaluations of the patients were performed during bed rest. Nausea levels, vomiting status and dizziness status of the patients were evaluated at the periods of 0-6, 6-24, and 24-48 hours. Analgesic and antiemetic drug consumption of the patients was

evaluated at the periods of 0-24 and 24-48 hours. Respiratory function evaluations of the patients were performed at the 24th and 48th hours.

Data analysis:

The data obtained from this study were evaluated by using the Statistical Package for the Social Sciences (SPSS, Inc., Chicago, IL, USA) 22.0 software program.

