After the data were transferred to the SPSS database, error controls were performed. Their compliance with a normal distribution was evaluated with Kolmogorov Smirnov test. The data determined were mean \pm standard deviation ($X \pm SS$), median and minimum-maximum (min-max) for the variables determined by the measurement and number (n) and percent (%) for the variables determined by counting. Since the variables determined by counting did not comply with a normal distribution, the difference between the three groups was evaluated by the Chi square test. The one-way ANOVA test was used to investigate the difference between the three groups regarding the measured values for values complying with normal distribution and the Kruskal-Wallis test was used for the values that did not comply with a normal distribution. The Bonferroni correction was implemented to determine the source of the difference in group comparisons. The Mann-Whitney U test was used to investigate the difference between two groups of variables. A p value <0.05 was accepted as statistically significant. The Paired Sample T Test was used for values complying with a normal distribution and the Wilcoxon Test was used for values not complying with a normal distribution when comparing the values of patients in the same group before and after the implementation.

Ethical consideration: Written permission and approval was obtained from the Gülhane Military Medical Academy's Head of Clinical Studies Ethics Committee before the study started. Physicians and nurses working at the Gülhane Military Medical Academy, General Surgery Clinic, Post-Operative Care Unit and Post-Anesthesia Care Unit within the Anesthesiology and Reanimation Clinic were informed of the study and verbal approval was obtained.

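### One p<0.05 rule covers every secondary outcome, with no adjustment across outcomes or time points and no exploratory label

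*Combined protocol and SAP*

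**What the plan says.** The opening paragraph makes pain and analgesic consumption primary. It lists the secondary outcomes as effects on "respiratory functions, vital signs, nausea and vomiting status, dizziness, antiemetic drug consumption, and saturation", with no order among them and no statement that they are exploratory.

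The Postoperative data collection section schedules most of these more than once:

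- "Nausea levels, vomiting status and dizziness status of the patients were evaluated at the periods of 0-6, 6-24, and 24-48 hours"
- "Respiratory function evaluations of the patients were performed at the 24th and 48th hours"
- Antiemetic consumption is totalled over 0-24 and 24-48 hours.
- Vital signs are read in the control arm at six postoperative times, and in the stimulation arms before and 30 minutes after each session.

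The Pulmonary function tests paragraph makes lung function two variables, PEF and FVC.

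The Data analysis section compares the three arms by chi-square, one-way ANOVA or Kruskal-Wallis. It adds Bonferroni to find the source of a difference between groups, and paired tests for before/after changes within an arm. It then states one rule: "A p value <0.05 was accepted as statistically significant". There is no repeated-measures model, no single summary per outcome, no testing order and no adjustment across outcomes or times.

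**The concern.** A three-group test at p<0.05 has a 5% chance of a false positive when there is no effect. Many such tests, all read against the same threshold, have a much larger chance of producing at least one. Leaving secondary outcomes unadjusted is common and acceptable when they are presented as supportive or exploratory. This plan instead gives any of them the label of statistical significance as soon as p falls below 0.05.

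What is at stake is what the trial may claim about its secondary outcomes. An isolated finding, such as less nausea in one period or a vital sign that differs at one hour, would carry the same label as a primary result. In an unblinded trial (Blinding paragraph), a reader could take it as an established effect of TENS or TAES. This point does not touch the conclusions on pain and analgesic consumption.

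**Working it through.** **The plan's own figures.** The documents give no family-wise error rate for the secondary outcomes, so there is none to reproduce. The only related calculation is the sample size: "Sixteen participants were required to detect an effect size of 1.4 at 80% power", with "The alpha level used to define significance was 0.05". A t-test calculation at d = 1.4 gives 8 per arm one-sided (16 in two arms, power 0.845) and 10 per arm two-sided (20 in two arms, power 0.841). The figure of 16 therefore matches exactly only as a one-sided, two-arm total, and the plan does not say whether it is a total or per arm. I assume 16 per arm in three arms ("A block randomization list was obtained for 3 groups"). The null error rate depends little on this choice.

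**Count of three-group tests, if each scheduled reading is tested once.**

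- PEF and FVC at 24 and 48 hours: 2 × 2 = 4
- Nausea, vomiting and dizziness in three periods: 3 × 3 = 9
- Antiemetic consumption in two windows: 2
- Subtotal: 4 + 9 + 2 = 15
- Vital signs: number not given. Assuming four at six times adds 4 × 6 = 24, giving 39.
- Saturation: no postoperative times given. Assuming the same six times gives 39 + 6 = 45.

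The within-arm before/after tests are not counted.

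**Independent tests.** The chance of at least one false positive is 1 − 0.95^m:

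- m = 15: 1 − 0.95^15 = 53.7%
- m = 39: 1 − 0.95^39 = 86.5%
- m = 45: 1 − 0.95^45 = 90.1%

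The expected number of false positives is 0.05m at any correlation: 15 × 0.05 = 0.75 and 39 × 0.05 = 1.95.

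**Correlated tests.** These come from 20,000 simulated null trials, with three arms of 16, normal outcomes, and an F-test at 0.05 for each reading. The same correlation is assumed between all readings:

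| Correlation | 15 tests | 39 tests |
|---|---|---|
| 0 | 53.5% | 86.4% |
| 0.3 | 46.3% | 74.4% |
| 0.5 | 37.4% | 58.2% |
| 0.8 | 21.8% | 29.6% |

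Repeat runs move these figures by about one percentage point, so I quote 21-54% and 30-86%.

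One common correlation of 0.8 is severe, since readings of different outcomes should agree less than repeat readings of the same one. With separate within-outcome and between-outcome correlations:

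| Within / between | 15 tests | 39 tests | 45 tests |
|---|---|---|---|
| 0.5 / 0.2 | 47.6% | 77% | 80.6% |
| 0.8 / 0.4 | 36.5% | 57% | 60.7% |

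Treating vomiting and dizziness as yes/no variables at 10-20% prevalence, tested by chi-square, changes the results by 3 points or less. The ANOVA simplification is therefore not driving them.

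**The case against.** The strongest reply is that the plan already separates primary from secondary outcomes, that unadjusted secondary results are common practice, and that nothing in the documents says how they will be interpreted. That is fair, and it makes this a matter of labelling rather than a flaw in the design. It does not remove the point, because the plan's only rule on interpretation attaches significance to any p below 0.05, secondary outcomes included.

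Four stronger readings are tempting, and the documents do not support them.

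- **That the plan tests every secondary outcome at every time.** It never says so. The schedule is a data-collection schedule, and separate testing is inferred from it together with the single-occasion tests. The inference is weakest for vital signs: the stimulation arms have two readings per session and the controls one per time, and the plan does not say which would be compared.
- **That a false positive is likely.** For the 15 countable tests the chance is about 37% at correlation 0.5, below even odds. It passes 50% in many settings only once vital signs are added, and their number is assumed.
- **That there is no multiplicity adjustment at all.** Bonferroni is named, for differences between arms.
- **That the plan breaks its own 5% error rate.** The stated 0.05 is a per-test threshold. An expected 0.75 false positives in 15 tests is exactly 5% per test, and nowhere is family-wise control promised for secondary outcomes.

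**Conclusion.** The point holds as a cheap improvement to the plan. The significance rule applies to all secondary outcomes alike, with nothing that accounts for the number of outcomes or times and no exploratory label. Under no effect, and if each scheduled reading is tested, the chance of at least one false significant secondary result is about 21-54% for 15 tests and about 30-86% for an assumed 39.

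These figures rest on three things the documents do not state: that readings are tested separately, that there are 16 patients per arm, and how strongly the readings correlate. The 39-test range also assumes four vital signs compared once at each of six times. The exact percentage is uncertain. The lowest is still high enough that a lone secondary p below 0.05 should not be read as an established effect.

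**What to change.** In Data analysis, restrict the p<0.05 rule to the primary outcomes. Add that all secondary outcomes, including every single-time and single-period comparison, are exploratory and will be reported as estimated differences between arms with confidence intervals and without a claim of significance.

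This needs no new data or patients. The cost is that no secondary result can be called statistically significant, however small its p-value. The change also does nothing about repeated testing of the primary outcomes, which is a separate matter.

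An optional alternative keeps some secondary claims: one summary per outcome over 0-48 hours for PEF, FVC, nausea, vomiting, dizziness and antiemetic total, with Holm across these six tests (smallest threshold 0.05/6 = 0.0083). It is not equivalent to the fix above:

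- It allows claims on the six summaries, while single-period results lose the label at any p-value.
- Summarising over 48 hours may dilute an effect confined to one period.
- As listed, it leaves vital signs and saturation outside formal testing although the plan names them as secondary, so a reason would have to be given.

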surgery. 4 electrodes were placed 2-3 cm lateral to the incision of the patients at the 30th minute and 2, 18, 22, 42, and 46th hours after the surgery and electrical stimulation was implemented at varying frequencies of 2-100 Hz for 30 minutes, at a maximum current intensity of 12 milliamperes that would not bother the patient or create muscle contractions, with a pulse duration of 0.25 min. . (Figure 1).

Second Intervention Group: The Patient Controlled Analgesia infusion was started right after the surgery. 4 electrodes were placed at the ST25, P6, ST36, and LI4 acupuncture points of the patients at the 30th minute and 2, 18, 22, 42, and 46th hours after the surgery and electrical stimulation was implemented at varying frequencies of 2-100 Hz for 30 minutes, at a maximum current intensity of 12 milliamperes that would not bother the patient or create muscle contractions, with a pulse duration of 0.25 min. (Figure 2).

Control Group: The Patient Controlled Analgesia infusion was started right after the surgery. No intervention was performed to the patients in the control group. The data of the patients were recorded at the post-operative 30th minute and 2, 18, 22, 42, and 46th hours. The flow chart of the study is shown in Figure 3.

The TENS device used in this study was a dual channel nerve stimulator. This device had 7 preset pain programs and 3 special programs. The program and the amplitude could be set individually for each channel. The electrodes of the device were 4x4 cm in size with 4 pieces in total. The electrodes were placed 2-3 cm lateral to the incision area and at the relevant acupuncture points. The current intensity was manually set according to the patient's tolerance.

Measurements

Baseline measurements

Preoperative measurements: The patients' age, gender, height, weight, diagnosis, history of a chronic sleep disorder and ASA class data were recorded. Pulmonary functions (PEF, FVC), vital signs, respiratory rate, saturation and pain level data were also recorded.

Outcome measurements

Intraoperative measurement: All patients received general anesthesia with the same protocol. The patients were observed during the surgical procedure and data such as incision length, duration of anesthesia, duration of surgery and number of drains were recorded.

Postoperative measurements: The medical findings of all patients after the surgical procedure were recorded.

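### The 'before' readings at 2, 22 and 46 h are not stimulation-free, so the within-arm before/after tests at those sessions can understate what stimulation achieves

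*Combined protocol and SAP*

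**What the plan says.** Under The interventions, both active arms are treated "at the 30th minute and 2, 18, 22, 42, and 46th hours after the surgery". Each session lasts half an hour. Under Postoperative data collection, vital signs and "pain levels of the patients who were included in the intervention groups before and 30 minutes after the implementation were evaluated". Controls have one reading at each time and no before/after pair: "pain levels of the patients in the control group were evaluated at the post-operative 30th min. and 2,18,22,42, and 46th hours".

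The Data analysis section uses these data in two ways. Within an arm, a paired t or Wilcoxon test applies "when comparing the values of patients in the same group before and after the implementation". Between arms, "The one-way ANOVA test was used to investigate the difference between the three groups regarding the measured values", with Kruskal-Wallis as the non-normal alternative, a Bonferroni correction, and Mann-Whitney for two groups. No washout, carry-over or choice of baseline is mentioned, and no change score is named for comparing arms.

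**The concern.** The sessions come in three close pairs: 0.5 and 2 h, 18 and 22 h, 42 and 46 h. The second session of each pair has a 'before' value taken soon after the first session ended. If that first session is still relieving pain, the 'before' value is already a treated value, and the change measures what the second session adds rather than what stimulation achieves against an untreated state.

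Pain is a primary outcome, and the paired tests are the only stated analysis of the effect of a single session. A small or non-significant change at 2, 22 or 46 h could be read as a session that did not work, when the explanation is that the previous one was still working. The same pairs of readings are used for vital signs. This is separate from the fact that a before/after test has no control.

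**Working it through.** **Timing (from the documents).** Session starts: 0.5, 2, 18, 22, 42, 46 h; session length 0.5 h. Gap to each 'before' reading = start minus (previous start + 0.5):

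- 0.5 h: no earlier session
- 2 h: 2 − 1.0 = 1.0 h
- 18 h: 18 − 2.5 = 15.5 h
- 22 h: 22 − 18.5 = 3.5 h
- 42 h: 42 − 22.5 = 19.5 h
- 46 h: 46 − 42.5 = 3.5 h

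Three of six 'before' readings therefore follow a session by 3.5 h or less. The plan states no figure of its own on this point, and its sample-size figure does not enter.

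**Direction (illustration; assumptions not in the documents).** Peak relief = 1, underlying pain flat, exponential decay with half-life H. Each session restores relief to the same ceiling and does not add to it. The plan does not say whether the 30-minute 'after' reading runs from the start or the end of the session, so both are shown.

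- Residual at the 'before' reading: r = 0.5^(gap/H)
- Change, 'after' at session end: 1 − r
- Change, 'after' 30 min later: 0.5^(0.5/H) − r
- Mean relief over 48 h, with full relief during the six sessions (3 h): [3 + (H/ln 2) × Σ(1 − 0.5^(g/H))]/48, where g runs over the gaps 1, 15.5, 3.5, 19.5, 3.5 and the last 1.5 h

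| Half-life | 1 h | 2 h | 4 h | 8 h |
|---|---|---|---|---|
| Residual at 2 h | 0.50 | 0.71 | 0.84 | 0.92 |
| Residual at 22 and 46 h | 0.09 | 0.30 | 0.55 | 0.74 |
| Mean six-session change, 'after' at session end | 0.887 | 0.782 | 0.661 | 0.527 |
| Mean six-session change, 'after' 30 min later | 0.594 | 0.623 | 0.578 | 0.484 |
| Mean relief over 48 h | 0.21 | 0.31 | 0.45 | 0.61 |
| Mean relief at the six 'before' readings | 0.11 | 0.22 | 0.34 | 0.47 |

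Example, session at 2 h, H = 1 h, 'after' 30 min later: 0.707 − 0.500 = 0.207, against 0.707 − 0 = 0.707 at the first session, a ratio of 0.29. The ratio is 0.16, 0.08 and 0.04 at 2, 4 and 8 h.

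**Without a ceiling.** If each session adds its full effect to whatever remains, the change with 'after' at session end is 1.00 at every half-life. With 'after' 30 min later, the mean change rises with half-life (0.67, 0.81, 0.89, 0.93). Neither version shrinks as relief lasts longer.

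**Which baseline works (ceiling model).**

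- First sessions only (0.5, 18, 42 h), 'after' at session end: mean change 1.00 at H = 1 h but 0.85 at H = 8 h, because 26% and 18% of peak relief remain at 18 and 42 h.
- Change from 18 to 22 h: 0.501 at H = 6 h, 0.477 at H = 8 h. From 42 to 46 h: 0.562 and 0.554. The longer-lasting method can still come out lower.
- Change from 0.5 to 2 h: equals the residual at 2 h, so 0.50, 0.71, 0.84, 0.92. It rises with duration because the 0.5 h reading precedes all stimulation.

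**The case against.** A reader might infer that the plan will rank a longer-lasting method below a shorter-lasting one. The documents do not support that. The quoted test is confined to one group and ranks nothing. Arms are compared on measured values, and at the common reading times lasting relief counts in favour of the method that provides it: in the illustration, mean relief at the six 'before' readings is 0.11 of peak at a 1 h half-life and 0.47 at 8 h, the correct order. A reversal needs someone to set the two arms' paired results side by side, or the term for measured values to be stretched to cover change scores, which the text neither states nor excludes.

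Nor does the change necessarily shrink as relief lasts longer. That needs a ceiling. One is plausible for pain, since the scale stops at 1 and all arms receive patient-controlled analgesia, but the documents do not establish it. Even with a ceiling, the change rises before it falls when the 'after' reading is 30 minutes after the session (0.594, 0.623, 0.578, 0.484).

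It can also be said that the paired change at a second session is a valid estimate of that session's increment. That is right; the understatement arises only when the increment is read as the full effect of stimulation. What remains is that three of the six 'before' values are not stimulation-free and the plan gives all six the same treatment without saying what the test estimates.

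**Conclusion.** The point holds in a limited form. The gaps of 1.0, 3.5 and 3.5 h follow exactly from the schedule if the listed times are session starts. That the paired tests at 2, 22 and 46 h can understate what stimulation achieves depends on two further conditions: relief outlasting the gap, and a ceiling on relief. The tabled figures show direction under stated assumptions and are not estimates for this trial. The size of the effect, and any loss of power, cannot be computed because the documents give no duration of relief, standard deviation or expected change. The planned between-arm comparisons of measured values are not undermined. The need is for a clear interpretation of the paired tests and a cleaner baseline for comparing arms.

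**What to change.** 1. In Data analysis, state that the within-arm before/after tests at 2, 22 and 46 h describe the increment of that session over any remaining effect of the previous one, that they are descriptive only, and that the two active arms will not be compared on them.
2. Use the 0.5 h reading, taken before any stimulation in all three arms, as the common baseline. Report the between-arm difference in change from 0.5 to 2 h, or compare the 2 h readings adjusted for the 0.5 h reading.
3. Compare the arms at 18, 22, 42 and 46 h adjusted for the same 0.5 h reading. Do not use changes from 18 to 22 h or from 42 to 46 h, since their starting values may carry residual effect.
4. Say whether the listed times are session starts, and whether the 30-minute 'after' reading runs from the start or the end of the session. Item 2 relies on the 0.5 h reading coming before the first session.

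All readings are already scheduled, so no new data are needed. The cost is a little more analysis work and fewer immediate-effect tests that can be read as the full effect of a session.
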